# 4. STUDY POPULATION

# 4.1 Population (base)

# 4.2 Inclusion criteria

To be eligible to participate in this study, a subject must meet all of the following criteria:

- Age of 18 years or older
- Life expectancy > 12 months
- Ability to provide informed consent

Additional criteria for cohort A:

• Partner of a participating patient

Additional criteria for cohort B:

- Histological diagnosis of a solid malignancy
- Treatment with monotherapy immune checkpoint inhibitor (ICI) against Programmed Death 1 (PD1) or its ligand PD-L1 (in curative or non-curative setting)
- Last ICI administration within 3 months of vaccination

Additional criteria for cohort C:

- Histological diagnosis of a solid malignancy
- Treatment with cytotoxic chemotherapy (monotherapy and combination chemotherapy is allowed, as well as a combination with radiotherapy, in curative or non-curative setting)
- Last chemotherapy administration within 4 weeks of vaccination

Additional criteria for cohort D:

- Histological diagnosis of a solid malignancy
- Treatment with a PD1 or PD-L1 antibody in combination with cytotoxic chemotherapy (in curative or non-curative setting)
- Last chemotherapy administration within 4 weeks of vaccination
- Last ICI administration within 3 months of vaccination

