#### 3. STUDY DESIGN

This is a prospective multicenter cohort study, designed to evaluate the immune response and safety after vaccination against COVID-19 in three cohorts with cancer patients and one cohort of participants without cancer (see Fig.1). The patient cohorts are defined by type of cancer treatment. Immunotherapy, chemotherapy and chemo-immunotherapy were chosen because these treatment regimens may affect the efficacy and safety of vaccination against COVID-19 in different ways.

Figure 1. Trial design

To reflect the real-world population of patients with cancer treated with immunotherapy and/or chemotherapy, this trial is designed as inclusive as possible. Exclusion criteria are minimal and serve to exclude patients who are not evaluable, or in whom vaccination is considered not safe or not effective. A cohort of volunteers without a cancer diagnosis is included for comparison. Because age is an important predictor of the ability to mount an effective immune response to vaccination [37], partners of patients are enrolled in cohort A. We will take care that from all patient cohorts partners are approached, until cohort A is complete. We anticipate that accrual of cohort A will be completed earlier than the patient cohorts.

All participants will receive two vaccinations against COVID-19 according to standard of care. Participants with an inadequate antibody response will be offered a third vaccination. To assess immune responses after vaccination, blood samples will be collected at baseline (i.e. prior to first vaccination), at the day of the second (and if applicable the third) vaccination and at day 28 after the second and third vaccination and 6, 11 and 18 months after the second vaccination by venipuncture. To evaluate hematology, with or without liver and kidney function, additional blood samples will be collected at baseline, at the day of the second and third vaccination, and at day 28 after the second and third vaccination and 6, 11 and 18 months after the second vaccination. Nasal mucosal lining fluid will be collected at baseline and at day 28 after the second vaccination according to a non-invasive sampling method.

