#### 10.1 Primary study parameter

The primary study parameter is the antibody based immune response to vaccination against COVID-19 on day 28 after the second vaccination in cancer patients as compared to individuals without cancer. SARS-CoV-2 S-specific serum IgG antibody concentrations will be measured at the RIVM using a validated fluorescent bead-based multiplex-immunoassay [40]. Geometric mean concentrations (GMCs) and 95% confidence intervals (CIs) will be calculated for the SARS-CoV-2 S-protein-specific IgG antibodies at baseline and day 28 after vaccination for each cohort. Participants will be classified as responders or non-responders. The definition of response is seroconversion defined as presence of SARS-CoV-2 spike S1-specific IgG antibodies with a threshold for seropositivity based on Receiver Operator Curve (ROC) analysis and set at 1.04 AU/mL [41]; in individuals without measurable anti-S antibodies at baseline. Concentrations have been interpolated from a reference consisting of pooled sera using a 5-parameter logistic

fit that was calibrated against the NIBSC/WHO COVID-19 reference serum 20/136 and expressed as international binding antibody units per ml (BAU/mL). The value of 1.04 AU/mL corresponds to 10 BAU/mL. Participants who are seropositive at baseline will not be included in the analysis of the primary endpoint. The percentage of responders and corresponding 95% CI for each cohort will be calculated. The percentage of responders of each patient cohort will be compared with the percentage responders in the group without cancer, using a modified standard fixed-delta test [42].

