#### **10.2 Secondary study parameters**

- Incidence and severity of solicited AEs during 7 days after each vaccination is a key secondary endpoint (see Appendix 1). Frequencies and absolute numbers of mild, moderate and severe solicited AEs per cohort will be listed for the first, second and third vaccination separately.
- The numbers, nature and severity of SAEs graded according CTCAEv5.0 will be listed per cohort.
- Incidence and nature of newly occurring irAEs grade ≥ 3 in cohorts B and D up to 28 days after the second vaccination is the second safety endpoint. irAEs will be graded according CTCAEv5.0. Frequencies and absolute numbers of all newly occurring irAEs grade ≥ 3 that occur between the first vaccination and 28 days after the second vaccination in cohorts B and D will be listed.
- Incidence, nature and severity of AESIs comprise the third safety endpoint. AESIs will be graded according CTCAEv5.0. Absolute numbers and frequencies of all AESIs will be listed per cohort and subdivided by severity.
- Levels of SARS-CoV-2 S-specific IgG antibodies at 28 days after the second vaccination will be compared between each patient cohort and the non-cancer cohort using ANOVA or Kruskal–Wallis one-way analysis of variance, and Welch ttests or Mann-Whitney U tests, depending on the distribution of the data.
- Levels of SARS-CoV-2 S-specific IgG antibodies before the second vaccination and at 6, 11 and 18months after the second vaccination will be measured to assess early antibody response and longevity. GMCs and 95% CIs will be calculated. The absolute numbers and percentages of responders will be reported for each cohort for each time point. Antibody levels before the second vaccination and at 6, 11 and 18 months will be compared between each patient cohort and the non-cancer cohort using ANOVA or Kruskal–Wallis one-way analysis of variance, and Welch t-tests or Mann-Whitney U tests, depending on the distribution of the data.

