SARS-CoV-2 specific T cell response will be measured at baseline, and at 28 days after the second and third vaccination, and 6, 11 and 18 months after the second vaccination and expressed as the number of IFN-γ producing SARS-CoV2 specific T cells/million PBMC. To assess the contribution of CD8+ T cells in this response, we will assess the number of IFN-γ producing T cells after blocking with an MHC class I antibody. This will be expressed as the number of IFN-γ producing CD4+ T cells/ million PBMCs. Subtraction of the number of responding CD4+ T cells from the total number of responding T cells will lead to the number of IFN-γ producing CD8+ T cells/ million PBMCs. Results will be compared between each patient cohort and the cohort of individuals without cancer using ANOVA or Kruskal–Wallis one-way analysis of variance, and Welch t-tests or Mann-Whitney U tests, depending on the distribution of the data.

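### Controls are partners of enrolled patients, but the antibody-level and T-cell tests in Section 10.2 treat the cohorts as independent, so their standard errors are probably slightly too wide

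*Combined protocol and SAP*

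**What the plan says.** Section 4.2 gives a single additional inclusion criterion for cohort A: "Partner of a participating patient". Section 3 gives age, as a predictor of vaccine response, as the reason why "partners of patients are enrolled in cohort A", and describes recruitment: "We will take care that from all patient cohorts partners are approached, until cohort A is complete". Controls are therefore linked one to one with patients, and the links are spread over cohorts B, C and D.

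Section 10.1 states for the primary endpoint that "The percentage of responders of each patient cohort will be compared with the percentage responders in the group without cancer", by a modified fixed-delta test. Section 10.2 compares antibody levels (before the second vaccination, at 28 days, and at 6, 11 and 18 months) and T-cell responses between each patient cohort and cohort A. It uses ANOVA or Kruskal-Wallis together with "Welch t-tests or Mann-Whitney U tests, depending on the distribution of the data".

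The opening of Section 10 promises to check the assumptions of each test and to report the results of those checks, but it does not name independence. No section mentions a couple or household identifier, a paired analysis, or clustered standard errors.

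**The concern.** The recruitment rule deliberately creates couples who share a predictor of the outcome. Each test named in Section 10.2 computes the variance of a contrast as the sum of two separate cohort variances. When some members of cohort A are partners of members of the comparison cohort, a covariance term belongs in that sum. If it is positive and left out, the standard error is too large, the p-values are too large and some power is lost. If it is negative, the error runs the other way.

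This matters most for the antibody and T-cell comparisons. They look for differences, so a conservative error is not a safeguard there as it is for non-inferiority. The outcomes are continuous and do not meet the ceiling seen in the responder percentages.

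**Working it through.** **Does the plan use the couples at the design stage?** Section 4.4 can be reproduced with the independent two-group formula n = (z₀.₉₅ + z₀.₈₀)² × [pA(1−pA) + pX(1−pX)] / (margin − true difference)², where (1.645 + 0.842)² = 6.183.

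- B versus A (90% and 90%, margin 10 points): 6.183 × 0.18 / 0.01 = 111.3, so 112 per group, as stated.
- C or D versus A, scenario 1 (90% and 60%, margin 40 points): 6.183 × 0.33 / 0.01 = 204.0, so 205 per group, as stated.

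Both figures come from treating the groups as independent.

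**Inputs for the continuous outcomes.** Evaluable numbers from Section 1.6: A 240, B 131, C 229, D 143. The documents give neither the number of couples per cohort nor a within-couple correlation, so these are assumptions:

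- Every evaluable control has an evaluable partner, and partners are spread over B, C and D in proportion to size. With 131 + 229 + 143 = 503 patients, the couples number 240 × 131/503 ≈ 63, 240 × 229/503 ≈ 109 and 240 × 143/503 ≈ 68.
- The variance on the analysis scale is equal in all cohorts.
- The within-couple correlation ρ is 0.1 to 0.3, with −0.1 shown for the opposite sign.

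**Formula.** With m couples inside a comparison, the variance of the mean difference is proportional to 1/nA + 1/nX − 2ρm/(nA·nX). Dividing by the independent value 1/nA + 1/nX gives

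variance ratio = 1 − 2ρm/(nA + nX), and SE ratio = its square root.

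| Contrast | 2m/(nA + nX) | SE ratio, ρ = 0.1 | SE ratio, ρ = 0.3 | SE ratio, ρ = −0.1 |
|---|---|---|---|---|
| B vs A | 126/371 = 0.340 | 0.983 | 0.948 | 1.017 |
| C vs A | 218/469 = 0.465 | 0.976 | 0.928 | 1.023 |
| D vs A | 136/383 = 0.355 | 0.982 | 0.945 | 1.018 |

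The true SE is thus about 2% to 7% smaller than the independent one when ρ is 0.1 to 0.3, and about 2% larger when ρ is −0.1. Section 10.2 states no significance level. If the tests were run at a two-sided 5% level, the actual rate would be 2Φ(−1.96/SE ratio): 4.6% at a ratio of 0.983, 3.5% at 0.928, and 5.5% at 1.023.

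**Sensitivity to equal variances.** If the patient SD were twice the control SD (an illustration), the ratio for C at ρ = 0.3 would be √[1 − (2 × 109 × 0.3 × 2)/(240 × 229) ÷ (1/240 + 4/229)] = 0.943 instead of 0.928.

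**Primary endpoint.** Section 1.6 reports 100% responders in cohort A. The variance in A is then zero, so the couple covariance is zero and pairing changes nothing. At the 300 BAU/mL cutoff (99.6% in A; 93.1%, 83.8% and 88.8% in B, C and D), the largest correlation that those percentages allow is about 0.23, 0.14 and 0.18. Even at those limits the SE falls by only 1.0% to 1.5%.

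**Non-inferiority at the planning rates.** Take 205 controls split 112:205:205, which gives about 44 couples in A versus B and 81 in each of the other two comparisons. With ρ of 0.1 to 0.3, the one-sided type I error of an independent test is 4.8% to 4.3% for B and 4.7% to 4.1% for C or D, against a nominal 5%. The power given up is 0.4 to 2.4 percentage points.

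**The case against.** The strongest reply is that this is a matter of efficiency. Partners were enrolled to make the groups comparable in age, and recruitment achieves that whether or not the analysis uses the pairs. The correlation is assumed. The couple counts are upper values, since not every evaluable control need have an evaluable partner (791 enrolled, 743 evaluable). The loss is small and, under positive correlation, conservative. All of that stands. It limits the size of the point but does not remove it: the tests in 10.2 assume independence, the recruitment rule puts that in doubt, and Section 10 itself undertakes to check assumptions.

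Several stronger readings are tempting, and the documents do not support them:

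- *The primary result is compromised.* It is not, because cohort A is at 100%. For D versus A (100% against 100%), an empirical couple-clustered variance would itself be zero. That the fixed-delta test assumes independence is also only inferred from the plan's wording and sample sizes, as its source is not available.
- *The standard errors are certainly too wide.* The sign depends on a correlation that the documents do not report.
- *Confidence intervals for the contrasts are wrong.* Section 10.2 plans tests between cohorts and intervals within each cohort. Correlation between cohorts leaves a within-cohort interval unchanged, so what is affected is the standard error behind each test, and hence its p-value and power.
- *The loss reaches 16%.* In cohort C, that would need all 229 patients to have a partner among the 240 controls, which conflicts with approaching partners from every patient cohort.
- *Household clustering invalidates the infection data.* Sections 3 and 10.3 make these data descriptive, with no test that assumes independence.

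**Conclusion.** The point holds as a minor one for the continuous outcomes in Section 10.2. The planned tests ignore a dependence that the design creates, and their standard errors are probably slightly too wide. The size, 2% to 7%, rests on ρ of 0.1 to 0.3, proportional spread of 240 controls with evaluable partners, and equal variances. Fewer complete couples, as is likely at later visits, would shrink it, and a negative ρ would reverse it. No false non-inferiority claim follows under positive correlation, and nothing in the reported primary result changes.

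**What to change.** Record a couple identifier linking each control to the enrolled partner. In Section 10.2, keep the planned tests and add, for each time point, an analysis of log antibody level and log T-cell count by cohort. Use a couple random effect or standard errors clustered on couple, and state in advance how zero T-cell counts are handled. Keep participants without an enrolled partner in the model: pairing is only partial in every contrast, so a simple paired test would not fit. Report the number of complete couples per contrast and the estimated within-couple correlation, which would settle the direction and the size. Leave Section 10.1 unchanged.

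The cost is one linkage variable and a small amount of extra analysis, with no new visits or samples. Eligibility for cohort A already requires knowing who the partner is, although the documents do not say that the link is stored in the dataset.

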# 4.3 Exclusion criteria

A potential subject who meets any of the following criteria will be excluded from participation in this study:

- Confirmed SARS-CoV-2 infection (current or previous)
- Women who are pregnant or breastfeeding
- Active hematologic malignancy
- Any immune deficiency not related to cancer or cancer treatment (e.g. inherited immune deficiency or known infection with Human Immunodeficiency Virus)
- Systemic treatment with corticosteroids (> 10 mg daily prednisone equivalent) or other immunosuppressive medication within 14 days of vaccination. Inhaled or topical steroids, and adrenal replacement steroids (> 10 mg daily prednisone equivalent) are permitted. In addition, standard of care with short course steroids to prevent nausea and allergic reactions from chemotherapy or iodinated CT contrast is allowed.

Additional criteria for cohort A:

- Current or previous diagnosis of a solid malignancy, unless treated with curative intent >5 years before enrolment and without signs of recurrence during proper follow-up
- Previous history of a hematologic malignancy

Additional criteria for cohort B:

- Treatment with cytotoxic chemotherapy within 4 weeks of vaccination Additional criteria for cohort C:
  - Treatment with an ICI within 3 months of vaccination

# 4.4 Sample size calculation

The primary endpoint is the antibody based immune response on day 28 after the second vaccination in patients receiving cancer treatment as compared to individuals without cancer. Participants are classified as responders or non-responders to vaccination against COVID-19. In patients treated with immunotherapy, we assume that the immune response rate is similar to that in individuals without cancer. In patients treated with chemotherapy or chemo-immunotherapy, we expect a lower immune response rate. As the percentage of responders is still unknown for vaccination against COVID-19, especially when a lower rate of immune response is expected, a power calculation for different scenarios has been performed, thereby comparing cohorts B, C, and D separately with cohort A.

#### Patients receiving immunotherapy (cohort B) vs. individuals without cancer (cohort A)

We assume that 90% of the individuals without cancer will be responders and that this will be similar in patients receiving immunotherapy. If there is truly no difference (90% responders in both groups), then 112 individuals without cancer and 112 patients are required to be 80% sure that the upper limit of a one-sided 95% confidence interval will exclude a difference in favor of the individuals without cancer of more than 10%.

# Patients receiving chemotherapy (cohort C) or chemo-immunotherapy (cohort D) vs. individuals without cancer (cohort A)

For patients receiving chemotherapy or chemo-immunotherapy, we expect a lower percentage of responders compared to the group without cancer based on influenza vaccination trials [29]. However, the percentage of responders is still unknown for vaccination against COVID-19. Therefore, we performed a power calculation for two different scenarios, 1) anticipated true response rate in the groups receiving

chemotherapy and chemo-immunotherapy of 60% and 2) anticipated true response rate in the groups receiving chemotherapy and chemo-immunotherapy of 40%.

Scenario 1: If there is a true difference in favor of the group without cancer of 30% (90% *vs.* 60%), then 205 individuals without cancer and 205 patients in cohort C and D are required to be 80% sure that the upper limit of a one-sided 95% confidence interval will exclude a difference in favor of the group without cancer of more than 40%.

Scenario 2: If there is a true difference in favor of the group without cancer of 50% (90% *vs.* 40%), then 205 individuals without cancer and 205 patients in cohort C and D are required to be 80% sure that the upper limit of a one-sided 95% confidence interval will exclude a difference in favor of the group without cancer of more than 50%.

In summary, these power calculations indicate that for the cohort C *vs.* cohort A comparison and for the cohort D *vs.* A comparison we need a total of 205 individuals without cancer , 205 patients treated with chemotherapy and 205 patients treated with chemo-immunotherapy. With these numbers we have enough power to assess non-inferiority in both scenarios with an alpha of 0.05 and 80% power.

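### Cohorts C and D have no single non-inferiority margin: section 4.4 prints 40 and 50 points, section 10.1 gives no delta, and Scenario 2 as printed has 5% power

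*Combined protocol and SAP*

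**What the plan says.** Section 4.4 sizes the three primary comparisons with cohort A separately.

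- **B vs A.** Both rates are taken as 90%. The upper one-sided 95% limit "will exclude a difference in favor of the individuals without cancer of more than 10" percent, with 112 per group and 80% power.
- **C or D vs A, Scenario 1.** "If there is a true difference in favor of the group without cancer of 30" percent (90% vs 60%), 205 per group give 80% assurance that the limit "will exclude a difference in favor of the group without cancer of more than 40" percent.
- **C or D vs A, Scenario 2.** "If there is a true difference in favor of the group without cancer of 50" percent (90% vs 40%), the same 205 per group give 80% assurance that the limit "will exclude a difference in favor of the group without cancer of more than 50" percent.

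The summary of that section concludes that "we have enough power to assess non-inferiority in both scenarios", with alpha 0.05 and 80% power. The same section says that the COVID-19 response rate is not yet known, which is why it uses scenarios.

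Section 10.1 gives the primary analysis: responder percentages with 95% confidence intervals per cohort, and a comparison of each patient cohort with A "using a modified standard fixed-delta test [42" (a literature reference). It states no delta for any cohort. Sections 2 and 8.1.1 state none either.

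**The concern.** A non-inferiority margin is the largest loss one is prepared to accept, fixed in advance. For B the plan has one such number. For C and D it has two, each attached to an assumption about the truth. No clinical reason is given for either, and no rule selects between them. Because the plan treats the true rate as unknown, nothing in it settles which limit applies before the data are seen. A fixed-delta test with no delta, set against two candidate limits, cannot be carried out as written.

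The size of the limits matters as well. A conclusion of non-inferiority under a 40- or 50-point limit means something quite different from the same word under B's 10 points, yet the plan uses one term for C and D and applies the same kind of rule to all three. A reader could take a result for C or D as reassurance that response under chemotherapy is close to that of controls.

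**Working it through.** **Inputs.** From section 4.4: 90% in A; 90% in B; 60% or 40% in C and D; limits of 10, 40 and 50 points; one-sided alpha 0.05; power 80%; 112 or 205 per group. From section 1.6: evaluable numbers 240 (A), 131 (B), 229 (C), 143 (D), and response 100%, 99.3%, 97.4%, 100%.

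**1. Reproduce the plan's sample sizes.** With unpooled variances,

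n = (1.645 + 0.842)² × [pA(1−pA) + pT(1−pT)] / (margin − true loss)².

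- B: 6.18 × (0.09 + 0.09) / 0.10² = 111.3, so 112. Matches.
- Scenario 1: 6.18 × (0.09 + 0.24) / (0.40 − 0.30)² = 204.0, so 205. Matches; power at 205 is 80.2%.
- Scenario 2 as printed: the denominator is (0.50 − 0.50)² = 0, so no finite n exists. Power at 205 is 5.0%, which is simply alpha.
- Scenario 2 with a 60-point limit: 6.18 × (0.09 + 0.24) / (0.60 − 0.50)² = 204.0, so 205, with power 80.2%.

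The printed 50 and the stated 80% power cannot both stand. A limit of 60 is what the calculation implies.

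**2. What each limit would accept.** With 205 per group, an observed 90% in A and the Wald limit,

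upper limit = (0.90 − pT) + 1.645 × √{[0.09 + pT(1−pT)] / 205}.

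- pT = 57%: 33.0 + 6.65 = 39.65 points, below 40, passes.
- pT = 56%: 34.0 + 6.66 = 40.66 points, fails.

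Setting the upper limit equal to the margin and solving for the observed loss gives:

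| Margin (points) | Largest passing loss (points) | Lowest passing rate against 90% |
|---|---|---|
| 10 (as for B) | 4.7 | about 85% |
| 40 (Scenario 1) | 33.3 | about 57% |
| 50 (Scenario 2 as printed) | 43.3 | about 47% |
| 60 (implied by n = 205) | 53.5 | about 37% |

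In whole counts, 185/205 vs 117/205 (57.1%) gives an upper limit of 39.80 points, and a score test against 40 points gives z = −1.72, so the boundary does not depend on the Wald form.

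**3. What a 10-point limit for C and D would have cost in power.** Power = Φ{(0.10 − loss)/SE − 1.645} at 205 per group: 95.8% if the true rate in C or D is 90%, 46% at 85%, 5% at 80%, and essentially zero at 60% or 40%.

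**4. Precision at Scenario 1.** 1.96 × √(0.33/205) = 7.9 points, the two-sided 95% half-width at 90% vs 60%.

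**5. Where the reported results fall.** I inferred counts from the rounded percentages in section 1.6: 240/240 (A), 130/131 (B), 223/229 (C), 143/143 (D). For B, 130/131 is 99.2% against the printed 99.3%, so that count is approximate. One-sided 95% score (Miettinen-Nurminen) upper limits for the loss against A are 3.4 (B), 5.0 (C) and 1.9 (D) points. For D vs A a Wald interval would have zero width, because both groups are at 100%.

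**The case against.** The strongest reply is that the scenarios were planning devices for an unknown response rate, that the cited method may define how the delta is set, and that the results are so close to 100% that no candidate limit changes a conclusion. The last part stands: the upper limits in step 5 lie well inside every limit discussed here. The first part does not rescue the text, since section 4.4 itself describes the scenarios as an assessment of non-inferiority with alpha and power. The cited method cannot be checked from the documents. Its exact boundary may differ slightly from 57%, but a citation does not tell the reader which of this trial's two limits applies.

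Four stronger readings are tempting and are not supported.

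- **That the margin is always the assumed loss plus 10 points.** That pattern is printed only for B (0 and 10) and Scenario 1 (30 and 40). Scenario 2 prints 50 and 50; plus 10 there is only what n = 205 implies.
- **That using 10 points for all three cohorts would cost nothing.** The high power holds only if C and D respond at about 90%, and the plan assumed 60% or 40%, where power is essentially zero. The documents also give no clinical basis for 10 points in patients on chemotherapy.
- **That the shortfalls at 300 BAU/mL in section 1.6 show the primary test to be too lenient.** That cutoff appears with the first results and is not the primary endpoint, which is seroconversion at 10 BAU/mL.
- **That the sponsor picked a limit to suit the data.** The documents show that the choice was left open, not that it was exploited.

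**Conclusion.** The concern holds in this form. The plan states no single decision rule for C vs A and D vs A, and one of the two printed scenarios contradicts its own power statement (5.0% against 80%). Under the smaller printed limit, an observed loss of up to 33.3 points would be called non-inferior, about seven times the 4.7 points that B's margin would allow at the same group size. These figures assume 205 evaluable per group, exactly 90% in A, and the one-sided 95% level that section 4.4 specifies; at a one-sided 2.5% level, 57% would narrowly fail 40 points (upper limit 40.92).

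The consequence is for what may be claimed, not for the observed percentages. A statement of non-inferiority for C or D has no identifiable pre-specified limit behind it. Section 1.6 shows that the primary results were known when this version was written, so a margin chosen now cannot repair that.

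**What to change.** **Section 4.4.** Present the C and D scenarios as precision statements, for example that 205 per group at 90% vs 60% gives a two-sided 95% half-width of 7.9 points. Correct Scenario 2: either the limit or the stated power must change.

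**Section 10.1.** State the 10-point delta for B vs A, which section 4.4 already contains. Report C vs A and D vs A as differences in responder percentage with score-type confidence intervals, which remain defined when both groups are at 100%. Drop the non-inferiority claim for C and D.

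**If a 10-point comparison is also shown for C and D,** date it, label it post hoc, and say that it has little or no power if the true response is as low as the plan assumed.

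**Cost.** Wording in two sections, with no new data and no change in sample size. The sponsor gives up the claim of non-inferiority for C and D against a pre-specified limit; the estimated differences and their intervals remain.

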## **1.6 First results VOICE trial**

Between February 17th and March 12th, 2021, 791 participants were enrolled in the current trial. For the primary endpoint at 28 days after the second vaccination, 743 participants were evaluable (per-protocol population): 240 individuals without cancer and 131 patients receiving immunotherapy, 229 patients receiving chemotherapy, and 143 patients receiving chemo-immunotherapy. SARS-CoV-2-binding antibody response (>10 binding antibody units (BAU)/mL) was found in 100%, 99.3%, 97.4%, and 100% of the participants in cohorts A, B, C, and D, respectively.

Given the importance for clinical decisions, we defined, based on neutralizing capacity, a cutoff level at 300 BAU/mL to discriminate between suboptimal and adequate responders. Twenty eight days after the second vaccination, 99.6% (A), 93.1% (B), 83.8% (C), and 88.8% (D) had an adequate response. Spike-specific T cell responses were detected in almost half of the suboptimal and non-responders. No new safety signals were observed [36].

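### Section 4.4, Scenario 2: the difference to be excluded (50 points) equals the assumed true difference (50 points), so the stated 80% power cannot hold; 60 points was probably meant

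*Combined protocol and SAP*

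**What the plan says.** Section 4.4 gives three non-inferiority calculations. Each states an assumed true difference in response rate, a limit that the upper bound of a one-sided 95% confidence interval should exclude, and a number per group for 80% assurance.

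- **Cohort B vs A.** 90% responders in both groups, so a true difference of 0. With 112 per group the interval "will exclude a difference in favor of the individuals without cancer of more than 10" percent.
- **Cohort C or D vs A, Scenario 1.** 90% vs 60%, a true difference of 30 points. With 205 per group the "confidence interval will exclude a difference in favor of the group without cancer of more than 40" percent.
- **Cohort C or D vs A, Scenario 2.** 90% vs 40%: "If there is a true difference in favor of the group without cancer of 50" percent, again with 205 per group. Here the "confidence interval will exclude a difference in favor of the group without cancer of more than 50" percent.

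The closing summary of the C and D calculations says: "With these numbers we have enough power to assess non-inferiority in both scenarios with an alpha of 0.05 and 80% power".

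Section 10.1 says that each patient cohort will be compared with cohort A "using a modified standard fixed-delta test" and gives no numeric limit. Section 4.4 is therefore the only place where limits for cohorts C and D appear as numbers.

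**The concern.** In Scenario 2 the difference to be ruled out is the difference assumed to be true. Power to exclude a value depends on the distance between that value and the truth. When the distance is zero, power equals the type I error rate, and a larger sample does not help. The 80% stated for Scenario 2, and the summary sentence that repeats it for both scenarios, are therefore incompatible with the printed limit.

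What is at stake is the accuracy of the documented design for two of the three primary comparisons. A reader of section 4.4 cannot establish whether the plan tolerated a deficit of up to 60 points with 80% power, or of up to 50 points with almost no power. These are different statements about what the trial was built to show.

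**Working it through.** **Inputs (section 4.4).** Response in cohort A: 90%. Response in patients: 90% (cohort B), 60% (Scenario 1), 40% (Scenario 2). One-sided alpha 0.05, power 80%, equal groups. Printed limits: 10, 40 and 50 points. Printed numbers per group: 112, 205 and 205, before the 20% increase for non-evaluable participants.

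**Formula.** Normal approximation with unpooled variance:

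n per group = (1.645 + 0.842)² × [pA(1 − pA) + pP(1 − pP)] / (limit − true difference)²

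The squared sum is 6.183, using unrounded normal quantiles.

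**Step 1: reproduce the plan's other figures.**

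| Calculation | Variance term | Limit − truth | n | Printed |
|---|---|---|---|---|
| Cohort B, 90/90, limit 10 | 0.09 + 0.09 = 0.18 | 0.10 | 111.29 → 112 | 112 |
| Scenario 1, 90/60, limit 40 | 0.09 + 0.24 = 0.33 | 0.10 | 204.02 → 205 | 205 |

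Both match, so this is evidently the method that was used.

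**Step 2: Scenario 2 as printed.** The variance term is again 0.09 + 0.24 = 0.33, but limit − truth = 0.50 − 0.50 = 0. The denominator is zero and no finite n exists.

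Power at 205 per group = Φ((limit − true difference)/SE − 1.645), with SE = √(0.33/205) = 0.0401:

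- Normal approximation: Φ(0 − 1.645) = 5.0%.
- Exact binomial enumeration of the Wald upper limit: 4.6%.
- The same enumeration with 1,000 per group: 4.8%.
- Variance restricted to the null hypothesis: 5.0%. Continuity correction: 3.5%. One-sided alpha 0.025: 2.5%.

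No variant comes near 80%.

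**Step 3: which limit would fit?**

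- A 60-point limit, 10 points beyond the truth as in the other two calculations: 6.183 × 0.33/0.10² = 204.02 → 205. Power at 205 is Φ(0.10/0.0401 − 1.645) = 80.2% (exact 80.6%).
- Solving for the limit that is excluded with 80% probability at 205 per group: 0.50 + (1.645 + 0.842) × 0.0401 = 0.600.
- Response rates of 60% and 40% have the same variance (0.24), which explains why 205 appears in both scenarios.
- Alternative: keep the 50-point limit and suppose that the response rate is the misprint, so 90% vs 50%. Then 6.183 × (0.09 + 0.25)/0.10² = 210.2 → 211, not 205. It also conflicts with the 40% rate, which section 4.4 states twice.

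**Step 4: does it affect the result?** Section 1.6 reports that a binding antibody response "was found in 100%, 99.3%, 97.4%, and 100% of the participants in cohorts A, B, C, and D", with 240, 131, 229 and 143 evaluable.

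- C vs A: 97.4% of 229 is 223/229, against 240/240. The difference is 2.6 points, SE = √(0.9738 × 0.0262/229) = 0.0106, and the one-sided 95% upper limit is 0.0262 + 1.645 × 0.0106 = 4.4 points.
- D vs A: 143/143 against 240/240. The Wald SE is zero, so a cautious bound is used instead. The deficit in D cannot exceed its non-response rate, whose exact one-sided 95% upper limit is 1 − 0.05^(1/143) = 2.1 points.

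Both lie far below 40, 50 and 60 points.

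**The case against.** The strongest reply is that this is one wrong digit that a statistical reader can repair. Two neighbouring calculations use a 10-point gap, and the same gap gives 60 points and exactly 205. On that reading the summary sentence is true, 205 is right, and nothing later in the plan changes. Scenario 1 alone supports 205, and hence 246 after the 20% increase. Enrolment was complete and the primary results were known when this text was current, and section 10.1 does not adopt the Scenario 2 limit as a decision margin. It could also be said that the reviewed text was extracted from a PDF and has character errors in other places, so the digit might differ on the sponsor's page.

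Much of this stands. The 60-point reading is strongly supported, the sample size is unaffected, and so is the conclusion. It does not remove the point. The inference is good, but no section states 60, so the correction cannot be confirmed from the document. The sentence is intact running prose with no sign of damage, although only the sponsor's copy can settle that. An 80% power claim beside a limit that permits about 5% is a wrong figure in the justification of the primary comparisons.

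One further caution is fair. The exact power figures describe a Wald interval, not the modified fixed-delta test named in section 10.1. The central argument does not depend on that choice, since section 4.4 states its claim in terms of a one-sided 95% confidence limit.

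**Conclusion.** The concern holds. As printed, Scenario 2 has power of about 5% (5.0% by normal approximation, 4.6% exact) against the 80% claimed, and no sample size would raise it. The summary claim of 80% power in both scenarios fails with it if the 50 is taken literally. The contradiction is certain and needs only the definition of a one-sided 95% limit. That 60 points was intended is an inference, resting on the 10-point gap in the other two calculations and the exact return of 205 (power 80.2%).

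The consequence is limited to the documented design. The planned 205 per group stands, and with the response rates in section 1.6 the primary conclusion is the same at any of the three limits. The text should be corrected, but the error casts no doubt on the findings.

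**What to change.** Retrieve the original sample size calculation and correct section 4.4 to agree with it.

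- **If 60 points was intended:** change the Scenario 2 limit to 60%. The 205 per group and the summary sentence stay as they are.
- **If 50 points was intended:** withdraw the 80% power claim for Scenario 2 and restrict the summary sentence to Scenario 1.

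In either case date the correction, as an erratum or through the amendment route in section 12.3, and state that the primary results in section 1.6 were already known, so that it is not mistaken for a margin chosen in advance.

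The cost is one look at the original calculation and a short text change. No participants are added, the sample size does not change, and nothing is re-analysed.
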